Next, the program was developed to reflect the availability and eligibility of services in one state (Tennessee); this decision was made because the adult service landscape differs from state to state. In the proposed project, we revise the curriculum to be nationally-relevant, by presenting aspects of each topic that are applicable across states and bringing in local experts to present information relative to their region. We also improve upon our study design by replacing a wait-list control with an active, materials-only control. The control group will receive the same written materials as the treatment group, but will not

receive the group-based training (they will have the option to participate in the training at the end of the study) This design improves upon our pilot work in two ways: (1) it will allow us to test whether receiving written information, without training, has similar benefits as the group-based program; and (2) it is more acceptable to participants. Though participants were not blinded, research staff facilitating completion of the surveys were blinded to experimental conditions.

2. Rationale and Specific Aims

An overview of the current study design is presented here (see Figure 2 below). We propose a multi-site (Nashville, TN; Chicagoland, IL; Madison/Milwaukee, WI) RCT of 180 families to test the effectiveness of ASSIST. Participants will be recruited in two cohorts and randomly assigned to either a treatment or materials-only control condition.

By randomly assigning participants to conditions, we reduce the likelihood of confounders that obscure treatment effects. Recruiting across three sites with diversity in community size, racial/ethnic make-up, and adult service systems will reduce bias due to unrepresentative samples.

We will also examine mechanisms of action and explore moderators of treatment response and barriers to participation. Our sample is sufficient to test our research questions (based on our statistical Power analysis). We will collect data from youth with ASD and their parents, to reduce informant bias. Post-randomization data collection will be conducted by personnel blinded to study condition. Based on existing research, we would expect that parents who receive the written materials might have some increase in knowledge about adult services, but likely not empowerment nor would we expect change in youth outcomes.

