The ASSIST program is a 12-week advocacy training to educate parents of youth with ASD about the adult service system. It is a group training, comprised of didactic instruction, family-sharing activities, case studies, and group discussions. Due to social distancing restrictions during the COVID-19 pandemic, the intervention will be conducted via web-conferencing. The ASSIST program for the proposed study will be directed at each site by an experienced Program Facilitator from the community with knowledge about group processes, person-centered planning, and adult service systems, who will be coached by a member of the study team. The ASSIST program will be delivered in full partnership with the local disability community. In most sessions, the Program Facilitator will be aided by community content experts who present the specifics of each topic. Experts will include representatives from the Parent Training and Information Centers, The Arc, the University Centers for Excellence in Developmental Disabilities, various

government agencies, attorneys, and parents of individuals with ASD. We have tentatively identified (and partially recruited) most of these community experts at each project site.

Finally, we take further steps to ensure that parental advocacy reflects the goals of the youth with ASD by: having a semi-structured discussion with the youth with ASD and their supporters about that youth's hopes, dreams, and goals prior to their parent taking the ASSIST program; developing individualized goals for transition outcomes from those discussions that will be used as an outcome measure; and including the youth with ASD in follow-up data collection to incorporate their perspective.

Specific Aims

Specific Aim 1. To use a multi-site RCT to examine whether ASSIST participation increases the intervention target of parent advocacy ability (defined by parental knowledge about adult service systems, advocacy skills, empowerment, and advocacy activities).

Hypothesis. Relative to a materials-only control group, ASSIST participation will lead to improvements in parental knowledge about adult services, advocacy skills, empowerment, and advocacy activities.

Specific Aim 2. To test whether participating in ASSIST leads to increases in employment, PSE, social participation, and access to services that facilitate these activities (number of services, unmet service needs, barriers), for youth with ASD transitioning from high school to young adulthood.

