After eligibility is determined and baseline data are collected, parents will be randomized, in two cohorts, to the treatment or materials-only control condition. Given the relatively small sample size in each cohort at each site ($n = 30$ at each of three sites), simple randomization is not recommended as it might result in unequal group sizes. We will use 1:1 block randomization within each site to give an equal number of subjects in each group. To ensure balance of important covariates, we will block on our key moderators: whether the youth has an intellectual disability (ID) and is in high school. Co-occurring ID and being in vs. out of high school impact service eligibility, and ID impacts the likelihood of PSE and community employment. By balancing moderators, we maximize our power to detect effect modification of the treatment effect; and we minimize the chance of having a very extreme distribution of important (moderating) covariates.

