1.0 Study Procedures

All data collection will occur in years 2019-2023 as explained below:

- Enrollment for the project is expected to occur in years 1-2.
- Cohort 1 (C1) Intervention group will take ASSIST from February-August 2020 (IL and TN sites; includes COVID break) and August-November 2020 (WI sites)

- C1 Control group will take ASSIST September-November 2021 (TN and IL Sites) and January-March 2022 (WI Site)
- Cohort 2 (C2) Intervention group will take ASSIST from August-Nov 2020 (TN and IL Sites) and November 2020-February 2021 (WI site)
 - C2 control group will take ASSIST from February-April 2022 (TN and IL) and March-May 2022 (WI sites).

Note: Due to social distancing restrictions, the in-person intervention series that began in February 2020 was paused between Spring 2020 to Summer 2020 for Cohort 1 intervention groups (TN and IL). In response to continued pandemic regulations, ASSIST was moved to synchronous web-conferencing in Summer 2020, and this method was the mode of delivery for all remaining sessions and series at all sites (TN, IL, WI)

A comprehensive characterization of each participant's circumstances and family context will be completed by administering a battery of direct assessments and informant report measures during the baseline visit. This visit will include structured observations, psychological testing, structured interviews, and questionnaires/surveys. Note that some of the survey measures will be offered to participants as web-links to be filled out at home or at the lab if social distancing restrictions allow. Paper copies of all surveys will be available based on participant preference.

Follow-up data collection points (post-intervention, 6, 12, 18, 24, and 30 months) may take place online or over the phone, depending on participants' preference and the included measures to be collected for that time-point. We will also make alternate methods of data collection available to youth with ASD for the interview, including video/text/online chat, as some participants with ASD may be more comfortable answering questions via chat than over the phone or web conference. The table of measures included in the *Procedures for Enrolled Families* section of this protocol, shows the longitudinal measures follow-up schedule for parent and youth participants.

5. Procedures

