Advocating for Supports to Improve Service Transitions (ASSIST)

NCT04173663

Statistical Analysis Plan

Document Date: 06/01/2022

STATISTICAL DESIGN AND POWER

Effects of the Intervention: Aims 1 and 2: Generalized linear models will be used to estimate the effect of treatment group assignment on each of the outcome variables considered. All models will include an indicator variable for treatment group and a treatment by time interaction while controlling for site and sex to improve the precision of the treatment effect estimate. We choose to model site as a fixed effect (2 d.f.) rather than a random effect because there are too few sites to have a stable estimate of a random effects variance.

For **Aim 1**, continuous outcomes (empowerment, advocacy skills, advocacy activities) will be modeled using linear regression and ordinal outcomes (knowledge) will be modeled using proportional odds ordinal logistic regression. The proportional odds model generalizes the non-parametric Wilcoxon rank sum test to a regression setting and is applicable to a wide variety of outcome types. However, we will consider parametric models for count data including Poisson and Negative Binomial regression if appropriate. In these cases, sensitivity analyses will be conducted to evaluate if our conclusions are robust to the choice of regression model.

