The general analysis plan for **Aim 2** will be identical to Aim 1, except indicators of youth outcomes will be considered. Continuous outcomes (e.g., social participation) will be modeled using linear regression, binary outcome (e.g., employment/PSE) will be modeled using logistic regression, and ordinal outcomes (e.g., number of services) will be modeled using proportional odds ordinal logistic regression (or another model, as specified in Aim 1). Time since beginning the VAP-T workshop will be the time scale of interest for all subjects, and we will flexibly model changes over time using restricted cubic splines. Significant changes over time will be assessed using likelihood ratios tests. For continuous outcomes, we will fit separate linear mixed effects models that include a random intercept to account for correlation arising from taking repeated measurements on the same subject over time. In sensitivity analyses we will use the Akaike Information Criterion to compare different models of the longitudinal correlation (e.g. random intercept, autoregressive, unstructured). For binary and ordinal longitudinal outcomes, we will use generalized estimating equations (GEE) and the robust Huber-White sandwich estimator clustering on participant identifier to account for longitudinal correlation. Analyses for Exploratory Aims 2a (using data collected from youth with ASD) and 2b (examining maintenance of treatment effects) will follow this same approach.

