Missing Data. An advantage to our proposed random effects longitudinal models is that they will readily incorporate both missing waves of data and mistimed measurements. In general, we will assume that data are missing-at-random (MAR) for the growth models and missing completely at random (MCAR) for binary and ordinal outcome models estimated using GEE and mediation analysis. Attrition analysis will be used to evaluate these assumptions. Analysis methods will also consider subjects who fail to complete the study (“dropouts”). Indirect information about the dropouts will be obtained by using binary logistic models to predict the probability of dropping out on the basis of all baseline predictor variables. When a variable is a significant predictor of dropout, the distribution of that variable differs for completers and subjects who drop out.

Power/Sample Size: We plan to recruit 180 subjects and after dropout expect to retain 162 subjects through initial post-test (Aim 1) and 152 subjects (76 per treatment group) through the 12-month follow-up (Aims 2 - 4). For power calculations, we consider baseline to post-test changes using the smaller sample size of 152. For continuous outcomes, the size of effect that we will have 80% power to detect will be impacted by the correlation between the pre and post measurement of the outcome. At worst ($r=0$), we will have 80% power to detect a 0.46 sd difference in continuous outcomes. If the correlation is 0.2 or 0.4, we will be able to detect a 0.29 or 0.17 sd difference, respectively. We believe these estimates are conservative because, from our pilot work, correlations between baseline and post-test scores of intervention targets were 0.56 (empowerment), 0.39 (advocacy skills), and 0.57 (knowledge). For binary outcomes, in pilot data, the probability of being employed or in PSE was about 0.5, so under this assumption we will have 80% power to detect a relative risk of 1.44. Regarding Aim 4, we will have 80% power to detect a 0.42 sd modification of the treatment effect assuming a $r=0.2$. All calculations assume a two-sided significance level of 0.05.

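### ASSIST is taught in groups in the treated arm only, but the models and power figures treat all participants as independent

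*Protocol*

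**What the plan says.** **Allocation.** Families are randomised individually (Protocol 4, Randomization): "We will use 1:1 block randomization within each site to give an equal number of subjects in each group".

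**Delivery.** Protocol 2 says of ASSIST: "It is a group training, comprised of didactic instruction, family-sharing activities, case studies, and group discussions". A Program Facilitator directs it at each site, helped by local content experts. The Study Procedures section schedules it by site and cohort. Controls receive the same written materials and may take the training only at the end of the study (Protocol 1). The number of training groups is not stated. Three sites and two cohorts suggest about six series, but references to intervention groups and WI sites in the plural leave room for more.

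**Analysis.** In the SAP (Aim 2, general analysis plan), models for continuous outcomes "include a random intercept to account for correlation arising from taking repeated measurements on the same subject over time". Binary and ordinal outcomes use GEE with a sandwich estimator, "clustering on participant identifier to account for longitudinal correlation". On site the SAP says: "We choose to model site as a fixed effect (2 d.f.) rather than a random effect because there are too few sites". Protocol 8 likewise refers only to repeated measurements over time.

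**Power.** SAP Power/Sample Size rests on 152 retained participants, 76 per arm, and gives a detectable difference of 0.46 SD at r = 0 and a relative risk of 1.44. Neither document mentions a training-group term, an ICC or a design effect.

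**The concern.** Treated parents share a facilitator, speakers and peers for 12 weeks, and controls do not. Any resulting similarity arises after randomisation and in one arm only (a partially nested design). A participant-level random intercept or participant-clustered sandwich cannot see it. A site main effect removes what both arms at a site have in common, not variation that exists only among treated groups.

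The planned standard error would then omit the between-group component, and intervals for the average effect across groups would be too narrow. That average is the quantity of interest if results are to carry over to new groups, and Protocol 2 looks forward to delivery by national organisations and state or local agencies.

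The concern is conditional. There is no inflation if the ICC is zero, or if ASSIST changes nothing for anyone. Inflation under a zero average effect requires group effects that vary around zero.

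**Working it through.** **Inputs from the documents.** Two-sided alpha 0.05, 80% power, 76 per arm, 0.46 SD at r = 0, relative risk 1.44 from a probability of 0.5 (SAP Power/Sample Size).

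**Assumptions.** G = 6 groups (3 sites x 2 cohorts), with G = 9 as an alternative; ICC 0.01 to 0.10.

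**Step 1: the plan's own figures.** (1.960 + 0.842) x sqrt(2/76) = 0.454 SD, or 0.457 SD with the t distribution, against the stated 0.46. For 0.50 versus 0.72 (relative risk 1.44), 76 per arm gives 80.0% power. Both reproduce with independent participants, so no clustering allowance is built in.

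**Step 2: variance with groups in the treated arm only.**
- Group size m = 76/G: 12.7 for G = 6, 8.4 for G = 9.
- Treated-arm design effect DE = 1 + (m - 1) x ICC.
- Variance inflation of the difference between arms V = (1 + DE)/2.
- Type I error of the planned test = 2 x [1 - Phi(1.96/sqrt(V))].
- Best-case detectable effect = 0.457 x sqrt(V).

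Example, G = 6, ICC 0.05: DE = 1 + 11.67 x 0.05 = 1.58; V = 1.29; sqrt(V) = 1.137; type I error = 2 x [1 - Phi(1.724)] = 8.5%; detectable effect = 0.457 x 1.137 = 0.52 SD.

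| ICC | V, G = 6 | Type I, G = 6 | Best-case SD, G = 6 | V, G = 9 | Type I, G = 9 |
|---|---|---|---|---|---|
| 0.01 | 1.06 | 5.7% | 0.47 | 1.04 | 5.4% |
| 0.02 | 1.12 | 6.4% | 0.48 | 1.07 | 5.9% |
| 0.05 | 1.29 | 8.5% | 0.52 | 1.19 | 7.2% |
| 0.10 | 1.58 | 11.9% | 0.58 | 1.37 | 9.4% |

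**Step 3: few groups.** An analysis that allows for grouping has few degrees of freedom. With v1 = DE/76 and v2 = 1/76, Satterthwaite df = (v1 + v2)^2 / [v1^2/(G - 1) + v2^2/75]. For G = 6 this gives 17.1, 15.7, 13.0 and 10.5 at the four ICCs. Detectable effects from the noncentral t are 0.50, 0.51, 0.56 and 0.63 SD (simulation: 0.50, 0.51, 0.57, 0.64). With nine groups they are 0.48, 0.49, 0.52 and 0.56 SD.

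**Step 4: does the site term help?** A site-adjusted regression was simulated with six treated groups and a zero average effect (20,000 trials per setting). False positives were 5.2% at ICC 0, 8.3% at 0.05 and 12.0% at 0.10. At ICC 0.05 the true SD of the estimate was 0.184 against a mean reported standard error of 0.161. Site adjustment does not remove the problem.

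**Step 5: binary outcome.** At a single time point, with probability 0.5, six groups and a participant-clustered sandwich, type I error is 5.0%, 5.6%, 7.7% and 11.3% at the four ICCs. Clustering by series without a small-sample correction still gives 7.1% to 8.2%. With a G/(G - 1) correction and a Satterthwaite t reference it is 4.8% to 5.0%.

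**Step 6: where the group effect must act.** In change scores with r = 0.5, a series effect constant from baseline leaves type I error at 4.8% to 5.1%, because it cancels. A series effect present only after baseline gives 5.8%, 6.4%, 8.3% and 11.7%.

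**The case against.** The strongest reply is that the harm depends on an ICC the documents do not give, and on an inferred number of groups. At an ICC of 0.01 to 0.02 the inflation is slight. Two of the measures marked primary, vocational and educational activities and service access, are youth outcomes further down the causal path, where the ICC may be smaller. This stands, and it limits how strongly the point can be put.

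Second, the inflation presumes that groups are a sample of future groups. The Protocol's dissemination aim is a rationale, not a defined estimand. That is fair, but an effect confined to these particular groups is a narrower claim than the Protocol wants to make.

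Third, the simulations use simpler tests than the planned multi-wave models with splines, so the percentages are illustrative. The missing variance component is the same.

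Fourth, r = 0 is the SAP's worst case. With baseline adjustment at r = 0.39 or 0.56, six groups and an ICC of 0.02, 0.454 x sqrt(1 - r^2 + 11.67 x ICC/2) gives 0.45 or 0.41 SD, within the stated 0.46; at an ICC of 0.05 it gives 0.49 or 0.45. This softens the absolute loss of power. It does not protect type I error: relative variance inflation at an ICC of 0.05 rises from 1.29 to between 1.34 and 1.42.

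Finally, about six groups give a poor estimate of the ICC. In simulation the 5th to 95th percentile range of the estimate was 0 to 0.09 when the true ICC was 0, and 0 to 0.17 when it was 0.05. Replacing the primary models on that basis is debatable. A pre-specified sensitivity analysis is not open to the same objection.

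**Conclusion.** The concern holds in its conditional form. The plan sets training-group correlation to exactly zero without saying so, and neither the site term nor participant-level clustering makes up for it. Under the assumed six groups, the consequence runs from minor (5.7% type I error at ICC 0.01) to more than double the nominal level (11.9% at ICC 0.10); nine groups reduce this to 5.4% and 9.4%. The plan should be changed, but this does not invalidate the design. Confidence in the practical size is medium, because both the ICC and the number of groups are assumptions and the ICC may differ by outcome or where sessions were accessed outside the group.

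The treated-arm-only description applies up to the 12-month assessment. Counting from the end of each treated series, the Study Procedures dates place control training after 12 months and before 18 months at every site and in both cohorts. For example, TN and IL cohort 1 treated series ended in August 2020, so 12 months falls in August 2021 and 18 months in February 2022; their controls trained in September to November 2021. Later assessments may therefore be clustered in both arms.

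**What to change.** **At minimum**, pre-specify the following as a sensitivity analysis for Aims 1 and 2:

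- Record each participant's training series. The SAP is dated after the scheduled series, so this is retrospective. If each site and cohort ran one series, it follows from site, cohort and arm.
- Continuous outcomes: add a random series effect in the treated arm only, acting on post-baseline measurements, with controls as singletons and Satterthwaite or Kenward-Roger degrees of freedom. A series intercept constant from baseline would cancel from the treatment-by-time contrast.
- Binary and ordinal outcomes: keep GEE, but cluster treated participants by series and controls individually, with a small-sample correction and a t reference.
- Treat controls as singletons only up to 12 months. From 18 months, assign controls who attended to their own series.
- Report the estimated ICC with its uncertainty, and restate the detectable effects over an ICC range, labelled as a best case.

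**Cost.** SAP wording, one variable, and modest model changes; randomisation, visits and data collection are untouched. Intervals widen. In the group-level analysis with six groups, simulated power at 0.46 SD falls to about 73%, 71%, 64% and 54% at ICC 0.01, 0.02, 0.05 and 0.10, and is 76% even at ICC 0. The SAP rejects a random site effect because three sites are too few, and six groups are only modestly better: the group variance is estimated at zero in about 51%, 44%, 30% and 16% of simulated trials at those four ICCs. A comparison of treated group means with individual controls, using Satterthwaite degrees of freedom, is therefore a useful check. Its simulated type I error was 5.3% to 5.4% with six groups and 5.0% to 5.1% with nine.

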Hypothesis. Relative to the materials-only control group, youth whose parents participate in ASSIST will have increased access to services and higher rates of employment, PSE, and social participation at 6-months and 12-months post-intervention.

Exploratory Aim 2a. We will examine whether ASSIST participation leads to enhanced goal attainment (as assessed by parents and youth with ASD), as well as better youth-reported quality of life and fit of employment/educational activities to the youth's skills and interests.

Exploratory Aim 2b. Using data collected 24-months and 30-months after intervention, we will examine whether treatment effects are maintained, strengthen, or wane.

Specific Aim 3. To examine which intervention targets (parent knowledge, advocacy skills, empowerment, advocacy activities) mediate the relations between ASSIST participation and youth outcomes of employment, PSE, social participation, service access, and goal attainment.

Hypothesis. In contrast to other intervention targets changed by ASSIST, parental empowerment will be the mechanism by which ASSIST participation leads to improvements in youth employment, PSE, social participation, service access, and goal attainment.

Exploratory Aim 4. To guide further adaptations of ASSIST, we will explore moderators of treatment response and barriers to participation in the intervention. We will explore factors that could relate to parents' ability to complete the ASSIST program and treatment

response, including: youth's intellectual functioning, pre- vs. post-high school exit, attendance at ASSIST sessions, socio-economic status, parental education, community size, family stress, and number of children with ASD in the family. We will also analyze qualitative data to inform future efforts to increase the accessibility of the ASSIST program for individuals with ASD.

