Goal identification (baseline) / Goal Attainment (FUs): Our team developed a goal bank that includes goals that fall into 5 categories: Employment & Post-Secondary Education, Daily living, Social and Spirituality, Healthy Living, and Safety & Security. This goal bank is a start point to help parents think about a vision for how their family member will live their life as an adult. The parent will select 5 potential goals from the goal bank, and work with a study team member to customize the selected goals during the baseline visit. After that, the youth will review the customized goals and/or select three of them that he/she is interested in (or create new customized goals if none of the goals the parent customized are of the youth's interest). Goals that are specified during this identification session will be scaled using Goal Attainment Scaling (GAS). GAS is an individualized outcome measure to calculate the extent to which specific goals are met by an individual. Goal selection will vary from participant to participant, but the goal scale will be standardized to measure goal attainment consistently across participants. During FUs, study staff will reach out to the parent participant and check in on the youth's goals' progress status.	X		X ^s			

Social Participation and employment correlates: The National Longitudinal Transition Study-2 (NLTS2) collected data over 10 years from parents, youth, and schools and provided a national picture of the experiences and achievements of young people as they transition into early adulthood. For the proposed research, we will use some of the questions developed for the NLTS2 concerning parent's social participation. In addition, we are including some questions developed to measure employment and social participation ([name], Adams, Bishop, 2017).
	X			X ^s				X

Satisfaction with Life Scale (SLS) - proxy report regarding son/daughter: the SLS (Diener et al., 1985) is a short 5-item measure of an individual's subjective quality of life. The SLS scale allows participants to integrate and weigh these domains in whatever way they choose. Participants rate their agreement with the 5 statements on a 7-point scale, from 1 (Strongly Disagree) to 7 (Strongly Agree).
	X			X ^s				X

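### Controls are scheduled to finish ASSIST before the 24- and 30-month visits, so a smaller arm difference there cannot by itself be read as waning (Exploratory Aim 2b)

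*Protocol*

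**What the plan says.** Protocol section 2 (Rationale and Specific Aims), Exploratory Aim 2b: "Using data collected 24-months and 30-months after intervention, we will examine whether treatment effects are maintained, strengthen, or wane".

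The protocol's background, just after the table of pilot limitations, says of the materials-only controls that "they will have the option to participate in the training at the end of the study".

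The protocol's 1.0 Study Procedures gives dated series for both arms:

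- Families assigned to training, first cohort: "Cohort 1 (C1) Intervention group will take ASSIST from February-August 2020 (IL and TN sites; includes COVID break) and August-November 2020 (WI sites"
- Families assigned to training, second cohort: "Cohort 2 (C2) Intervention group will take ASSIST from August-Nov 2020 (TN and IL Sites) and November 2020-February 2021 (WI site"
- Families assigned to materials only, first cohort: "C1 Control group will take ASSIST September-November 2021 (TN and IL Sites) and January-March 2022 (WI Site"
- Families assigned to materials only, second cohort: "C2 control group will take ASSIST from February-April 2022 (TN and IL) and March-May 2022 (WI sites"

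In the measures tables of Protocol section 5, the parent vocational-educational and service-access interviews are repeated at 24 months (T5) and 30 months (T6). Several other measures are repeated at T6, among them "Social Participation and employment correlates", the parent empowerment scale and the youth life-satisfaction scale.

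The SAP, under Aims 1 and 2, says: "All models will include an indicator variable for treatment group and a treatment by time interaction". Its Aim 2 paragraph applies the same approach to Aim 2b.

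**The concern.** The background text leads a reader to take the 24- and 30-month data as ASSIST against written materials only. The dated calendar says otherwise: by those visits, any control family that took up the offer has been trained. Neither document mentions control uptake, a time-varying exposure, censoring at control training, or a different estimand for the late visits.

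Aim 2b has three possible answers: the effect persists, grows or fades. If trained controls benefit, the gap between arms narrows even when nothing is lost in the intervention arm. A reader of the planned treatment-by-time result could then report fading when the controls had caught up.

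**Working it through.** **Dates.** The inputs are the series months in 1.0 Study Procedures. The aim counts visits from after the intervention, while the SAP counts time from the beginning of the workshop, so both clocks are checked. The formula is: gap = (clock origin + 24 or 30 months) − last month of the control series. Example, Cohort 1 TN/IL from series end: August 2020 + 24 months = August 2022; controls finish in November 2021; gap = 9 months.

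In the last three columns the first figure counts from series end and the second from series start. All figures are in months.

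| Group | Intervention | Control | Series end to control end | Control end to T5 | Control end to T6 | T3 (12 months) to control start |
|---|---|---|---|---|---|---|
| C1 TN/IL | Feb–Aug 2020 | Sep–Nov 2021 | 15 | 9 / 3 | 15 / 9 | 1 / 7 |
| C1 WI | Aug–Nov 2020 | Jan–Mar 2022 | 16 | 8 / 5 | 14 / 11 | 2 / 5 |
| C2 TN/IL | Aug–Nov 2020 | Feb–Apr 2022 | 17 | 7 / 4 | 13 / 10 | 3 / 6 |
| C2 WI | Nov 2020–Feb 2021 | Mar–May 2022 | 15 | 9 / 6 | 15 / 12 | 1 / 4 |

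Every T5 and T6 visit follows the end of control training on either clock. Every T3 visit, and so every 6-month visit, precedes its start.

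The 18-month visit (T4) is not part of Aim 2b, and its position depends on the clock. From series end it falls 3, 2, 1 and 3 months after control training ends (groups in table order). From series start it falls one month before control training begins in C1 TN/IL, one month after its first month in C1 WI, in its first month in C2 TN/IL, and in its last month in C2 WI.

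**Size, as an illustration.** The plan's binary case is a risk of about 0.5 and a relative risk of 1.44, that is 0.72 against 0.50, with 76 per arm. Reproducing its power with a two-proportion z test and pooled null variance:

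- 0.22 × √76 = 1.918
- 1.96 × √(2 × 0.61 × 0.39) = 1.352
- √(0.50 × 0.50 + 0.72 × 0.28) = 0.672
- (1.918 − 1.352) / 0.672 = 0.84, which gives 80% power, as stated.

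Now let the effect last in the intervention arm. Let a share u of controls train, and let each gain a fraction b of the effect. The control risk becomes 0.50 + 0.22 × u × b, and the relative risk 0.72 / (0.50 + 0.22 × u × b). Both u and b are assumptions, since the documents give neither.

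| Uptake u | b = 1: control risk, RR | Difference (points) | b = 0.5: control risk, RR | Difference (points) |
|---|---|---|---|---|
| 25% | 0.555, 1.30 | 16.5 | 0.5275, 1.36 | 19.25 |
| 50% | 0.61, 1.18 | 11 | 0.555, 1.30 | 16.5 |
| 75% | 0.665, 1.08 | 5.5 | 0.5825, 1.24 | 13.75 |
| 100% | 0.72, 1.00 | 0 | 0.61, 1.18 | 11 |

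In every row the intervention arm has lost nothing. No late power figure is offered, because retention to 24 and 30 months is not stated.

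**The case against.** The strongest reply has four parts.

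- **The aim is exploratory, and the randomised comparison remains valid.** Both are true. It stays a fair comparison of two policies, but they are not the two policies that the aim names.
- **Control training is optional, so the distortion may be small.** True. The bias is conditional on uptake and on trained controls benefiting. Even so, the plan's own hypothesis is that ASSIST improves youth outcomes by 6 and 12 months, so benefit in trained controls is what the plan would expect.
- **A treatment-by-time model gives both fitted trajectories, so one can see whether the intervention arm fell or the controls rose.** This stands in part. The trajectories are informative, but that reading is descriptive and not protected by randomisation: age, high-school exit and calendar time all move with it.
- **If controls are in fact trained only after the last visit, as the background sentence can be read, there is no problem.** That is correct, but the dated calendar says otherwise, and the documents do not settle it.

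Two stronger readings are tempting and not supported. A reader might infer that the 6- and 12-month results are contaminated, directly or because late visits enter the same spline. Those visits precede control training on either clock. The SAP gives no knots and does not say whether late waves enter that fit, so no spill-over can be sized. A reader might also infer that the design supports no long-term claim at all. If trained controls benefit, a maintained or larger late difference is conservative and remains interpretable.

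**Conclusion.** The point holds in a limited form. On the protocol's calendar, the T5 and T6 arm contrast compares immediate with optional delayed ASSIST, not ASSIST with materials only, in all four cohort-by-site groups. If trained controls benefit, a lasting effect is biased toward apparent waning, and a smaller late difference cannot be attributed to fading from the arm contrast alone.

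The size is unknown. The illustration runs from little change to complete disappearance of the difference, and it starts from the plan's detectable effect, which is not a forecast. The conclusion assumes that the calendar was followed and that some controls accepted the offer. Severity is minor: the aim is exploratory, and the 6- and 12-month window that carries the main hypotheses is clean as scheduled.

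**What to change.** 1. In the SAP, define the T5/T6 comparison, and any T4 visit after control training starts, as *immediate versus optional delayed ASSIST*. Report control uptake and training dates beside it. State that a reduced arm difference will not be read as waning. Show each arm's course from T3 to T5/T6 as a descriptive, non-randomised supplement.
2. Reconcile the background statement on when controls may train with the dated calendar in Study Procedures.
3. As a secondary sensitivity check only, refit the 6- and 12-month effects using visits through T3. Note its price: it drops later-wave information that the SAP's mixed models would use under missing-at-random.

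The cost is SAP wording plus a record of uptake and dates; no visit or measure is added. The real concession is that Aim 2b gives up a randomised ASSIST-versus-materials statement about waning beyond 12 months.
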